The primary endpoint will be a composite adherence outcome determined by dried blood spot intracellular tenofovir diphosphate (TFV-DP) levels. A subject will be considered adherent if the TFV-DP levels are above 1246 fmol/punch (consistent with 7 doses in past week) at both week 12 and the last study visit over the 48 weeks. All randomized subjects that were dispensed PrEP at baseline will be included in the modified intent-to-treat analysis. Participants not achieving week 12 will be considered non-adherent.

Secondary Adherence Endpoints

A key secondary endpoint will be a composite outcome determined by TFV-DP levels at both week 12 and the last study visit associated with adequate adherence (>719 fmol/punch).

Self-reported adherence to PrEP through 48 weeks is defined as the proportion of text-reported doses over all possible doses in 48 weeks. Missing responses due to either missed text messages or early discontinuation of the study will be considered as no doses taken. Sensitivity analysis will also be done on the 'as-treated' population (i.e. treat missing as missing).

Additional self-reported adherence measure will be >90% adherence (i.e. on the ACTG 4-day recall at weeks 12, 24, 36, and 48); >90% dosing by VAS at each study visit.

- Poor adherence is defined as < 4 doses a week or discontinuation of study drugs. Subgroup analysis will explore the endpoint for discontinuation for reasons other than lack of risk or confirmed adverse event.
- Safety and tolerability outcomes are defined as incidence rates of: i) discontinuation of TDF/ FTC for any toxicity; ii) grade 2 or higher adverse event (symptoms or laboratory toxicity); iii) serious adverse events; iv) death

Randomization and Stratification

Subjects will be randomized (1:1) to one of two arms: the **iTAB** or the **iTAB+MI-B** enhanced adherence arm. Randomization will be stratified by clinic site, sex assigned at birth (male vs female), and prior history of PrEP use. Participants assigned "intersex" at birth will be included in the female group. A total of 300 subjects (150 per arm) will be randomized and followed in the study for 48 weeks after enrollment of the last subject.

Once eligibility and consent are confirmed, randomization will occur using the web-based CCTG data management system.

Study Power and Sample Size Justification

The study is powered to compare the primary adherence rate between the two study arms using a two-sample, two-sided proportion test. Expected drug-level adherence based on a previous study of MSM using iTAB for PrEP for this composite endpoint (>=1246) was 33%. Assuming the adherence rate of the transgender iTAB alone group will be the same the study has 77% power to detect a difference of 16% between the iTAB+MI group and the iTAB alone group, with 150 subjects per group.

Monitoring

The study team will review all adverse events during PrEP therapy as cumulative reports in both arms combined, on monthly team calls. Adverse events will be graded using the ACTG toxicity grading scale and recorded using standard CCTG AE electronic data capture. An independent Data Safety and Monitoring Board (DSMB) will not be used for this study because the drugs are licensed for this indication and relatively non-toxic.

Statistical Analysis Plan

In general, analyses of efficacy will incorporate the modified intent-to-treat (mITT) principle, namely, all randomized participants dispensed study medication will be included in the analysis. For all secondary analyses of efficacy, no adjustments for multiple comparisons will be made and a p-value of 0.05 will be considered statistically significant. Analyses of safety will be focused on "as treated" populations.

Demographic and baseline measurement variables will be summarized via standard descriptive statistics. There will be no interim analyses for futility or efficacy conducted.

Analysis of Primary Outcome

Descriptive analysis will be performed on the primary adherence outcome via a frequency table and Fisher's exact test. Logistic regression modeling will be conducted to assess the group differences while adjusting for potential covariates.

Analysis of additional Secondary outcomes

Descriptive analysis will be performed for all the secondary outcomes. For comparisons between the two study arms, Fisher's exact test will be used for categorical outcomes; t-test or Wilcoxon rank sum test will be used for continuous outcomes. Multivariable logistic regression model will be used to study factors associated with poor adherence. Factors will include demographics, substance use, untreated mental illness, socieconomic status, low health/HIV and system literacy, fear of disclosure and non-English language. To evaluate changes in risk behavior after initiation of PrEP, descriptive summary will be provided for the number of HIV positive/unknown status partners and any unprotected anal intercourse with an HIV positive/unknown status partner by visit (at w12, 24, 36 and 48). Wilcoxon signed rank test will be used for comparison at each follow-up visit to the baseline visit. GEE model will be used to assess the change in risk behavior over time.

Safety analysis

Safety data will be reported for all the randomized subjects while they were taking or immediately (30 days) after taking study drug (as treated analysis). Tables will summarize the number of serious adverse events, adverse events (grade 2 or higher), PrEP discontinuation due to adverse events, by study arms and overall. Fisher's exact test will be used to compare the rates between the two groups. The time to TDF/FTC discontinuation due to adverse events will be compared between groups using the log-rank test and plotted using Kaplan-Meier curves.

SUB-STUDY I DESIGN

This pharmacologic sub-study will use the main study cohort to determine the interaction of cross-sex hormone therapy (csHT) on PrEP efficacy as measured by TFV-DP and FTC-TP DBS intracellular levels, and of PrEP on csHT effectiveness as measured by quantitative hormone levels in plasma.

SUB-STUDY I PROCEDURES

Subjects will be consented for participation in the sub-study at the main study's Screening Visit.

As part of the main study, plasma and DBS samples will be collected at Baseline and every 12 weeks. A Baseline DBS sample will be collected only if the subject is already on PrEP at the time of Baseline. Detailed concomitant hormone use, including route and frequency, will be collected at every clinic visit. Daily iTab responses will be used as a self-reported adherence measure.

At Weeks 0, 12, and 48, applicable subjects will complete the Body Image Scale (mBIS) questionnaire, and answer questions about general hormone therapy satisfaction.

SUB-STUDY STATISTICAL CONSIDERATIONS

Sample Size and Power

The primary aim of this analysis is to determine if PrEP interacts with hormone therapy in either direction that would impact either i) efficacy of PrEP to reduce HIV acquisition or ii) hormones to achieve desirable gender traits. Of our 300 person cohort, we estimate that 280 individuals will be MAAB Of those 280 MAAB, we predict that 70% will be taking feminizing hormones (n=196) and 30% will be on no hormonal therapy (n=84), based on previous population estimates (97). Based on adherence results in individuals randomized to iTAB (98), we estimate that 25% of participants will have perfect adherence to PrEP.

[figure not shown]

Figure 2: Predicted Numbers of Individuals on HRT and PrEP

Statistical power is based on a one-sample non-inferiority test to see if the TFV-DP concentration of perfectly adhered MAAB persons is equivalent to MSMs on average under an acceptable margin. The following assumptions are made: i) Using PK modeling of HIV-uninfected men and women, it has been shown that perfect adherers (i.e. daily dosing for 7 days) have TFV-DP concentrations of 1560 (IQR 1246-2029) fmol/punch as determined in MSM; ii) Since this is a non-inferiority study, we will assume the expected sample mean for MAAB is around 1560 fmol/punch, or slightly lower. In other words, we will assume the mean difference in TFV-DP concentrations between MAAB and MSMs is approximately 0 (ranges from -180 to 50); and iii) We believe that a difference of less than 230 fmol/punch (equivalent to 1 tablet per week dosing) in the TFV-DP concentration can be considered non-inferiority which will be the lower limit of acceptable variation. Thus, we will set the non-inferiority margin to be 230.

Assuming the standard deviation is 350, if the true mean TFV-DP concentration for MAAB is 1360 fmol/punch (ie, 100 fmol/punch lower than MSMs), then 45 subjects are required to be 80% confident that the lower limit of a one-sided 95% confidence interval of the mean difference between MAAB and MSMs will be above the non-inferiority limit of -230.

Analysis Plan

The primary outcome is the intracellular TFV-DP levels, as measured in DBS, which is a continuous variable. Comparison between the MAAB and the existing MSM data that will be compared using a two-sample t-test. Differences in the means between the two groups, along with the standard deviations (SD) and their 95% confidence intervals will be reported. As a secondary/sensitivity analysis, multiple regression analysis will be performed to study the association between clinical and demographic factors (age, race, ethnicity, education, socioeconomic status, sexual risk behaviors, substance use, depression, concomitant medications) and group, adjusting for baseline demographic, stratification variables, and clinical characteristics. Variables significantly associated with both group and outcome (p<0.10) will be included in a multiple regression model as covariates.

For the main secondary hypothesis, in MAAB on csHT, to determine the change between baseline and week 12 estradiol levels in individuals taking PrEP and receiving stable estrogen replacement (controlling for route, dose and formulation), we will use a paired t-test. As estradiol concentrations can be unpredictable, we will measure estradiol concentrations in individuals choosing not to initiate PrEP at the same time points. Similar to 3A, multiple regression models will be developed if there are factors that require adjustment in this model.

Other secondary analyses will explore further interactions between PrEP and csHT in MAAB we will perform analyses of the following potential interactions: a) TFV-DP in transgender persons (MAAB and FAAB) of all adherence levels compared to not taking csHT, b) TFV-DP in MAAB taking versus not taking antiandrogen medications (i.e. spironolactone and finasteride) and c) emtricitabine-triphosphate (FTC-TP) concentrations (recent adherence measure) in transgender persons of all adherence levels taking versus not taking hormones. These analyses will be analogous to the descriptive analyses in the primary outcomes. For FAAB transgender individuals, to determine the change between baseline and week 12 testosterone levels in individuals taking PrEP and receiving stable testosterone replacement (controlling for route, dose and formulation), we will use a paired test. For hormone therapy satisfaction, the main outcome of interest to these individuals is maintaining the physically desirable characteristics that the csHT provide. Thus, it is not the hormone levels that are as important

as the satisfaction with these traits. For the entire cohort of MAAB who are on stable csHT dosing (as defined as no change from baseline to week 12) from baseline to week 12 and from baseline to week 48 we will compare the hormone satisfaction with physical traits ranked for satisfaction using the BIS and summed for overall satisfaction score to compare between weeks 0, 12 and 48. Similarly, we will use the BIS for FAAB on stable csHT assessing physical traits compared at weeks 0, 12 and 48.

SUB-STUDY IV PROCEDURES

At Baseline, eligible participants will consent for additional sub-study sample collection on the main study informed consent form. Genital collection for *Neisseria gonorrhoeae* and *C. trachomatis* will be done at Baseline and Week 24 as part of the main study STI screening procedures.

For the sub-study, two genital swabs for microbiome and cytokine testing will be collected at Baseline and Week 24. Additional genital swabs for a vaginitis multiplex assay, herpesvirus and HPV testing as well as CVF collection via aspirator for TFV levels will be collected at Week 24.

Sub-study IV	Study Weeks of Follow-up					
Schedule of Evaluations	Screen	Wk 0	Wk 24			
Window	14 days	30 days	+/- 4 weeks			
Informed Consent	Х					
CV swab for cytokine testing		Х	Х			
CV Swab for microbiome		Х	X			
CVF collection for drug concentration TFV			X			
Vaginal swab for herpesvirus and HPV			X			
Vaginal swab for vaginitis multicomplex			X			

Sub-study IV Statistical Considerations

Aim 1: To determine the impact of pro-inflammatory STIs on CVF TFV levels.

We will quantify CVF TFV levels of participants at week 24 and compare levels in those with and without the presence of active vaginal infections using methods for continuous measures (i.e., the Student t test or Wilcoxon test depending on distributions). The primary analysis will compare those with any infection to those with no detected infection. We will examine individual organisms in subanalysis. We will also compare the proportion of participants with TFV levels in steady state (\geq 50 ng/mL) to those with levels that are not (<50 ng/mL) at week 24 for vaginal infections using Fisher's exact test. The threshold of \geq 50 ng/mL was selected based on previously reported CVF steady state trough concentrations at 24 hours achieved by oral dosing (\leq 11).

Sample Size: Based on an estimated mean concentration of 119 ng/mL and a standard deviation of 58 ng/mL in CVF TFV in a steady state PK study(32), we have 80% power with a one-sided lower bound alpha of 0.05 to detect a difference in individuals with STIs versus those without STIs of 33 ng/mL or 28% reduction in CVF TFV levels in a sample of n=40.

Aim 2: To determine the impact of CV inflammation on CVF TFV levels.

We will compare TFV levels as a continuous measure with \log_{10} -transformed cytokine levels at week 24 using the Pearson correlation test or Spearman correlation test if they are not normally distributed. For assessment of chronic inflammation and TFV levels, we will compare those with and without elevated cytokine levels of at least one cytokine (MIP-1 α and β , IP-10, IL-6 and IL-8) that remains higher at both baseline and week 24 using Student t-test or Wilcoxon depending on distributions. If cytokine levels are below the level of detection in \geq 40% of samples, these will be converted to categorical variables (detectable versus undetectable).

Exploratory Aim: To assess the impact of the CV microbiome on CVF TFV levels.

Sequence Analysis: We will use Quantitative Insights into Microbial Ecology (QIIME) to perform taxonomic dependent and independent classification.(33) While with taxonomic dependent classification we can investigate the dynamics of specific group of bacteria (i.e. *Lactobacillales*) in relation to clinical and immunological variables, taxonomic independent classification will provide measures of total microbial community composition. We will classify bacteria at the order level and we will use the alpha diversity as measurement of diversity. We will characterize (cross-sectionally) the composition of the CV microbiome in our study groups and determine any associations with TFV levels. We will describe species diversity in participants with TFV levels ≥50 ng/mL and

levels <50 ng/mL at week 24. Associations between cytokine concentrations and STIs with the presence or absence of vaginal microbiota species will be assessed using Student t-tests.

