- 3. To compare self-reported adherence to TDF/FTC in the iTAB+MI-B versus iTAB arms over 48 weeks using
 - a) adherence defined as "the proportion of text-reported doses over all possible doses over 48 weeks"; missing text messages or early discontinuation of the study will be considered as no doses taken
 - b) a continuous measure of the percentage of days adherent by self reported measures (iTAB, cumulative 3 day recall, and the visual analog scale) in an "as treated" analysis for those that are retained on study
- c) stratified analysis of 3a and 3b outcomes within male-assigned at birth and female-assigned at birth groups
- 4. To compare study retention between arms, defined as the proportion of participants that complete all study visits regardless of whether they were on drug or not
- 5. To determine factors associated with poor adherence (< 719 fmol/punch over 48 weeks) and discontinuation of TDF/FTC
 - Factors considered to be associated with poor adherence to TDF/FTC will include demographics, socioeconomic status, perception of HIV risk, ongoing substance use, intimate partner violence, low health/HIV and health systems literacy, and stigma
- 6. To determine the rate of linkage and continuation of TDF/FTC at 12 weeks after study completion between arms
- 7. To determine the rate of HIV seroconversion in TDF/FTC-using transgender / gender non-confirming individuals and compare the proportion of seroconversions over 48 weeks between arms
- 8. To measure the acquisition of other sexually transmitted infections (STIs) and compare rates of acquisition of new STIs at any site between arms
- 9. To evaluate changes in risk behavior after PrEP initiation (risk compensation) by comparing the numbers of HIV positive partners, partners of unknown HIV status, unprotected insertive and receptive anal or vaginal acts between Baseline and subsequent visits
- 10. To evaluate the safety and tolerability of daily TDF/FTC as PrEP as measured by discontinuations due to
 - a) any adverse events
 - b) serious adverse events and
 - c) grade 2 or higher adverse events

Sub-study I Primary Objective: To determine whether csHT interacts with PrEP in male-assigned at birth (MAAB) persons that would affect efficacy of PrEP, measured by intracellular TDF concentrations in DBS.

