For participants with disqualifying safety laboratory results, the study coordinator will instruct the participant to immediately cease study medication and an interim screen failure visit will be scheduled at the clinic. The following procedures will be conducted at the screen failure visit:

- Participant will return any remaining study medications.
- Participants with disqualifying creatinine or creatinine clearance values may request to re-screen into the study but may not repeat a same-day PrEP initiation visit.
- If HBsAg positive, the participant will be referred to care.
- If HIV positive, study coordinators will follow the procedures outlined in 6.11.4 and 6.11.5 in the Protocol.
- Participant will be terminated from the study as a Screen Failure.

In-Clinic Study Visits (Weeks 12, 24, 36, and 48; approximately 1 hour)

Participants will be asked to return to the clinic at week 12 and every 12 weeks up to week 48. Study visit procedures include:

- Assessment of adverse events since last contact.
- Targeted medical history and physical examination, including collecting weight
- Review of concomitant medications, including detailed csHT use
- Laboratory evaluations
 - Rapid HIV screening
 - 3-site (throat, rectal, urine) STI NAAT screening for gonorrhea and chlamydia (weeks 24 and 48 only)
 - Syphilis RPR (weeks 24 and 48 only)
 - Calculated creatinine clearance (Cockcroft-Gault)
 - Plasma hormone levels for participants on csHT (week 12 only, sub-study only)
 - Urine β-HCG for participants capable of being pregnant.
- Sample collection for banking
 - Dried blood spot (DBS) for participants on PrEP
 - Whole blood, plasma, and serum
 - Urine
 - Rectal swabs (week 48 only)
- CASI assessments
- Medication dispensation. Participants will be provided enough medication to last until the next scheduled visit through the investigational pharmacy. Participants will not be provided PrEP at week 48.
- Risk reduction and medication adherence counseling. Counseling will not be performed at week 48.
- End of Study assessment (week 48 only). This survey will assess participant's experiences over the course of the study, including changes in their medical insurance status, access to other healthcare services, changes in perceptions of PrEP and of their own health, and their opinions about the intervention.

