- Ability to access and maintain their PrEP regimen since EOS
- Ability to access health insurance coverage since EOS
- If participant has not accessed PrEP and/or does not have health insurance, the participant will be asked for their reasons and possible barriers to uptake
- Adherence (if on PrEP)
- HIV risk behavior
- Perceptions of PrEP efficacy

Schedule of Evaluations for Subjects On-study, Off-medications

At any point of the study, participants may elect to stop study medication but remain on study. Participants not on study medication will follow the same schedule as defined in the schedule of evaluations until the end of study, with the following exceptions:

- Medication will not be dispensed
- Adherence counseling and monitoring of medications will not be performed
- DBS will not be collected
- iTAB account for participant will be switched to "inactive"

		Study Weeks of Follow-up								Interim ⁷	
Schedule of Evaluations	Screen	Wk 0	Same-day PrEP	2	12, 24, 36	48 / EOS	48 EXT ◊	60	Visit	Phone	
Window		30 days		+/- 1 week	+/- 4 weeks			+/- 4 weeks			
Informed Consent	Χ		Х								
Inclusion / Exclusion	Χ		Х								
Randomization		Χ	Х								
iTAB setup		Χ	X								

Medical/medication										1
history and targeted	Χ	Х	X		X	X	X		Χ	
physical exam										
HIV risk reduction		X	Х		Х		X			
counseling										
Adherence counseling ¹		Χ	X		X		Х			
TFV/FTC dispensed ¹		X	Χ		Х		Х		(X)	
Telephone follow-up				Χ				X		Χ
Adverse events				Х	Х	Х			(X)	(X)
assessment ¹				,,	^	^			(71)	(71)
Computer assisted self-	Х	Х	X		Х	Х				
interview (CASI) surveys	,,	,								
End of Study survey						Х				
Post-study survey						 		Χ		
Laboratory										
HIV EIA / NAT or Ag/Ab	Х		Х		(X) ²		(X) ²		(X) ²	
test					(^)		(^)		(^)	
HBsAg	Χ		X							
Creatinine and GFR	Х		X		Х	X	X			
(calculated CrCl) ¹					^	^	^			
Urinalysis	X		X							
Urine β-HCG ³	X	Χ	Х		X	X			(X)	
CBC, liver enzymes		Х	Х							
Rapid HIV		Х	Х		X	X	X		(X)	
STI screen [†] : GC, CT,		X	Х		X ⁵	X			(X)	
syphilis		^	^		Λ	^			` ,	
GC Treatment [†]									(X)	
Plasma hormone levels ⁴		Χ	Х		(X)					
Dried Blood Spot (DBS) ¹		(X) ⁶	(X) ⁶		X	X			(X)	
Banked whole blood,		Х	Х		Х	Х				1
serum, plasma										
Banked urine		Χ	X		X	X				
Banked rectal swabs		Х	Х			Х				
(x2)		^	^			^				
HIV confirmatory test if	(X)		Х		(X)	(X)	(X)	(X)	(X)	
HIV+	(//)				(//)	(//)	(//)	(//)	(//)	
CD4, HIV RNA, and HIV										
genotype if HIV+ after			Χ		(X)	(X)	(X)	(X)	(X)	
baseline										

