¹ Only for participants curre	ently taking	n PrFP Pai	rticinants red	uirina PrFI	P dispensation dur	ing an Interi	m visit v	vill rece	ive enou	ah PrFP

Only for participants currently taking PrEP. Participants requiring PrEP dispensation during an Interim visit will receive enough PrEP to last until the next regular study visit.

Adherence and Behavioral Assessments

We will measure adherence using the self-report daily text messages. These texts will include a personalized lead-in reminder message (e.g., "Those who are closest to you care about your health") and participants will be asked "Did you take your dose today? Reply: Y) Yes N) No P) Postpone". If 'Postpone' is selected, participants will receive a follow-up message 1 hour later asking them if they took their medication (Yes or No). Participants will also have the option of determining the word used to describe the study drug (e.g., 'med', 'dose', or other personal choice). Nonresponse or a 'No' response will be counted as not taking their dose. At each follow-up

² Participants with medication interruption greater than 14 days will require confirmation of HIV seronegative status prior to re-initiation of PrEP. Re-initiation must be achieved prior to the end of the week 36 visit.

³ Only for participants capable of becoming pregnant

⁴ Only for participants currently taking csHT. Baseline and Week 12 only.

⁵ STI screen only at week 24

⁶ Week 0 DBS collected only if participant is already taking PrEP at Baseline

⁷ Interim visit for: HIV testing if off PrEP for over 1 week and had high risk event, consider NAT or Ab/Ag; STI testing only if has symptoms (urethral discharge, genital sore); if seroconverted outside study; adverse event assessment

[†] UCSD-only sub-study evaluation. Additional specimens will be collected from anatomic site of positive GC at time of treatment. ♦ UCSD-only study extension

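### The plan contradicts itself on whether adverse events are assessed after a participant stops PrEP, which puts the endpoint of discontinuation due to adverse events at risk

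*Combined protocol and SAP*

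**What the plan says.** All places are in section 9 unless stated otherwise.

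- **Schedule of Evaluations, footnote 1.** The adverse event row and the creatinine row are both marked with this footnote: "Only for participants currently taking PrEP".
- **In-Clinic Study Visits (Weeks 12, 24, 36, and 48).** The list includes "Assessment of adverse events since last contact", with no on-drug condition. The same list does set that condition for another item: "Dried blood spot (DBS) for participants on PrEP".
- **Schedule of Evaluations for Subjects On-study, Off-medications.** "Participants not on study medication will follow the same schedule as defined in the schedule of evaluations until the end of study", apart from four exceptions: dispensing, adherence counseling with medication monitoring, DBS, and the iTAB account. Adverse event assessment and creatinine are not among them.
- **Safety analysis.** "Safety data will be reported for all the randomized subjects while they were taking or immediately (30 days) after taking study drug". The section also plans a log-rank comparison and Kaplan-Meier curves for time to discontinuation due to adverse events.
- **Section 6, Secondary Objective 10.** "To evaluate the safety and tolerability of daily TDF/FTC as PrEP as measured by discontinuations due to" any, serious, or grade 2 or higher adverse events.

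**The concern.** The participants whom footnote 1 would leave out are those who define the endpoint. Someone who stops at week 14 because of a side effect and attends week 24 off drug has no adverse event assessment at that visit under the table. The event behind the stop may then go unrecorded, or the stop may be put down to another cause. The 30 days after the last dose, which the safety analysis says it will report, are by definition spent off drug.

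At stake are Objective 10, the incidence of discontinuation for toxicity listed among the safety and tolerability outcomes, and the time-to-discontinuation analysis. A misattributed stop would also move into the planned subgroup of discontinuations for reasons other than lack of risk or a confirmed adverse event. There is no independent DSMB, and the study team's monthly review relies on the adverse events that are collected.

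**Working it through.** The plan states no figure on this point, so the check is to set the texts side by side and ask what each means for an attendee who is off drug.

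| Place | Adverse events assessed? |
|---|---|
| Schedule table, footnote 1 | No |
| In-clinic visit list, weeks 12 to 48 | Yes, back to last contact |
| Off-medication rules | Yes, because not excepted; but they refer the reader back to the schedule |
| Footnote 7, interim visits | A listed purpose ("if seroconverted outside study; adverse event assessment"), but the table entries are conditional and the row carries footnote 1 |
| Safety analysis | Needed through 30 days after the last dose |

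**Step 1. Does the marker look deliberate?** Five rows carry footnote 1: adherence counseling, dispensing, DBS, adverse events and creatinine. The first three match the off-medication exceptions. Adverse events and creatinine do not, and the in-clinic list gives both without condition. This suggests that the marker is misplaced on those two rows, but it does not prove it.

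**Step 2. Does any rule settle the conflict?** The Statistical Considerations section gives the SAP precedence over that section's own wording. I found no rule for a conflict between the schedule table and the visit narrative. Sites could therefore reasonably act differently.

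**Step 3. How does the 30-day window fall relative to visits?** Assume that the stopping day is uniform between two visits. The share of stoppers whose whole 30-day window closes before the next visit is (gap − 30) / gap.

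- Planned spacing, 12 weeks = 84 days: (84 − 30) / 84 = 54 / 84 = 64%.
- Shortest gap under the ±4 week windows, 84 − 56 = 28 days: shorter than 30 days, so 0%.
- Longest gap, 84 + 56 = 140 days: (140 − 30) / 140 = 110 / 140 = 79%.

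At the planned spacing, then, about two thirds of between-visit stoppers have the whole window behind them at the next visit, and its capture at scheduled visits rests on the look-back there. For the rest, the window is still open at that visit. In both cases, under the literal footnote, nothing is elicited at the visit if the person is still off drug. Under the in-clinic list, the events since last contact are elicited. This is an illustration of timing, not an estimate of how many events are lost.

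**Step 4. Direction of any bias.** An event that is not elicited cannot be recorded as the cause of a stop. The effect is to understate discontinuation due to adverse events, and so to make tolerability look better.

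**The case against.** The strongest reply is that the current text already requires the assessment. The in-clinic list is unconditional, and since it restricts DBS to people on PrEP, the lack of a restriction on adverse events looks intended. The off-medication rules do not remove the assessment. A site that follows the narrative captures the events. This stands, and it means that the finding is a contradiction and not an established loss.

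Other routes may also catch some events. The medical history and targeted examination carry no footnote and take place at weeks 12, 24, 36 and 48. A person with a side effect may make contact while still on drug, and adverse event assessment is a named purpose of interim visits. The planned subgroup by reason for discontinuation presupposes that reasons are recorded somewhere. These points reduce the likely loss. But a medical history is not a designated adverse event assessment, and the interim entries are conditional and under the same footnote.

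The text also refers to a fuller protocol and a procedures manual. Whether stopping triggers its own assessment there cannot be determined from what is available.

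Finally, the reach is limited. The primary and key secondary endpoints are drug levels, both arms receive the same licensed drug, and safety is one of ten secondary objectives. That stands too. None of it tells a site which text to follow.

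**Conclusion.** The documents contradict themselves on whether adverse events are assessed after a participant stops PrEP. If sites follow the table, events that led to stopping and those in the next 30 days may not be formally elicited at the next visit, and discontinuation due to adverse events would be biased toward better tolerability. The contradiction is certain from the text; the loss is conditional on site practice. It is worth correcting because a named secondary objective depends on it and the correction is cheap.

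Three stronger readings are tempting and are not supported:

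- *That these events are missed.* The in-clinic list and the off-medication rules both point the other way.
- *That a number of participants can be given.* Assumed stopping rates of 10% to 30% would give 0.10 × 300 = 30 to 0.30 × 300 = 90 stoppers, but the documents give no such rate. Not every stop is due to an adverse event, some participants will resume before the next visit, and some sites will follow the narrative. The number affected cannot be derived.
- *That the comparison between arms is biased.* The footnote is the same in both arms. Telephone counseling in the iTAB+MI-B arm might bring out more side effects, but the documents do not link those calls to adverse event recording.

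**What to change.** Remove footnote 1 from the adverse event row, so that the table agrees with the in-clinic list, the off-medication rules and the safety analysis. If the sponsor does not want adverse event collection at every off-drug visit to week 48, the minimum is to reword the footnote for that row so that it covers events since last contact through 30 days after the last dose. In either case, add that the reason for stopping is recorded at the first contact after a stop; none of the passages compared here states this.

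The creatinine row has the same conflict with the in-clinic list and the off-medication rules, and those texts must be reconciled.

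Two related points should be checked in the same edit. The adverse event row is blank in the extension column, although the extension visit list includes the assessment. It is also blank at week 60, and the list for that call does not mention adverse events. So for participants who take drug up to week 48 and do not enter the extension, no scheduled assessment covers the 30 days after the last dose, whichever way footnote 1 is read.

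The cost is one footnote edit and slightly more adverse event data entry at visits already attended.
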